- Feasibility. We will calculate the percentage of participants who a) meet the inclusion criteria, b) agree to be randomly assigned, c) complete the full tDCS protocol, and d) attend the follow-up assessment.
- Acceptability. We will collect data on participants' tDCS experience via a questionnaire, at the conclusion of tDCS treatment on a 0 (strongly disagree) to 10 (strongly agree) scale: 1) It was easy to prepare the device and accessories; 2) The device was unnecessarily complex; 3) The device was easy to use; 4) I felt the video conferences with a technical person were helpful; 5) I would imagine that most people would learn to use this device quickly; 6) The device was cumbersome to use; 7) I felt confident using the device; 8) I needed to learn a lot of things before I could get going with this device; 9) The effectiveness of the treatment increased over the course of treatment; 10) Overall, I felt that transcranial electrical stimulation treatment benefited me. Participants will also be encouraged to elaborate their answers in free-form.
- Moreover, we will evaluate the presence and severity of possible side effects of treatment at the end of each session on a 0 (not at all) to 10 (highest degree) scale. The participants will be asked in an open-ended manner whether they experienced any side effects, and they will then be asked specifically about tingling, itching sensation, burning sensation, pain at the stimulation site, fatigue, nervousness, headache, difficulty concentrating, mood change, and changes in vision or visual perception. If any side effects are reported, the degree of relatedness to the intervention will be assessed on a 5-point scale (details of the data and safety monitoring plan are provided in the Human Subjects section). This approach has been used in our previous study and frequently in other studies.

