The SMC will comprise 3 members with expertise in neuromodulation, statistics, and geriatric clinical research: [name], professor of psychiatry and behavioral sciences at Baylor College of Medicine; [name], PhD, associate professor and biostatistician at The University of Texas Health Science Center at Houston Cizik School of Nursing; and [name], Roy M. and Phyllis Gough Huffington Chair in Gerontology and the Nancy P. and Vincent F. Guinee Distinguished Chair in Gerontology at The University of Texas Health Science Center at Houston. The SMC members are independent of the project. These members are appropriately qualified to review the scientific design and conduct of the study, to evaluate safety and risks to participants, to interpret data statistically, and to make recommendations concerning continuation, modification, suspension, or termination of the study.

Annual SMC meetings will begin after the first week of data collection. In addition, should any adverse event occur, the SMC will be informed immediately, and a special session will be scheduled to discuss strategies to deal with the event. The annual meeting will include a synopsis of the protocol and design, discussion of the status of interventions and data collection procedures, a summary of subject contacts, discussion of any adverse events or potential adverse events, status of data entry and verification, and a summary of any descriptive and inferential statistics to date. Details about data quality and completeness and data collection timeliness will be provided to the SMC, including enrollment rates, exclusion rates and reasons, completion of scheduled data collection, reasons for study withdrawal, adequacy of enrollment composition, demographic similarities/differences between the intervention and control groups, protocol deviations and adherence, and compromises in confidentiality. The SMC meetings will be closed sessions without the investigators, during which the SMC will discuss the need for additional procedures to prevent adverse events or ensure data integrity. In the unlikely case that the study needs to be terminated early owing to unexpected adverse events or inadequate conduct of the study, the SMC will make recommendations to the investigators.

Recommendations from the SMC meetings will be shared with the UTHealth IRB and the NIH during annual reports and immediately if the SMC identifies adverse events not previously reported or recommends early termination of the study.

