## B. DSM Procedures

### B1. Monitoring study safety.

Monitoring schedule. All the stimulation and testing sessions will be supervised by trained research staff who will monitor potential adverse events and symptoms. At each stimulation, participants will be asked to report any adverse events they have experienced. A study physician (i.e., [name]) will also be available to evaluate the participant if needed. Based on information obtained at this visit, participants will then be referred for follow-up assessment and/or treatment with the appropriate healthcare provider. Drs. [name], [name], [name], and [name] will meet every month (by phone and/or in person) to monitor study progress including data collected from participants on any serious health events that caused them to seek medical attention and if any of these resulted in hospitalizations overnight. Any adverse reactions noted by any of the team members will be reported to the PI, the UTHealth IRB, SMC, and NINR. All adverse events will be reviewed monthly by the research team and annually by the SMC. Also, in keeping with NIH guidelines, minority status and gender will be included in these reports to allow for the detection of differential effects.

Auditing selected cases for compliance with IRB requirements. All data designated as primary outcome data will be subject to a 100% cross-referencing between electronic and paper forms. This audit must have an error rate less than 1%. If the verification fails the audit, all data will be re-entered, the original computer files will be discarded, and the newly re-entered data will be audited. This process will continue until the audit no longer exceeds the maximum allowable error rate. All audits will be supervised and documented by the PI.

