Adverse event reporting. Study participants will be encouraged to immediately report any "emergencies or events" by calling the study contact number. These instructions will be included on the consent forms. The study team will record all reported events in the adverse events and unanticipated problems log (including the subject's name, the date, and an event description). All members of the study team will inform the PI, [name], immediately of any adverse events and unanticipated problems, and he will consult with co-investigators and the SMC members on the necessary action. The PI will report the incident to the UTHealth IRB within one week. The action and date of implementation will also be recorded in the adverse events and unanticipated problems log. The entire investigative team and SMC will participate in classifying events as "serious" or "non-serious" (see list below), as well as "non-attributable," "possibly attributable," or "attributable" to the intervention. The SMC will advise the PI and the study team on actions to be taken to minimize further adverse events and unanticipated problems within 2 weeks of reviewing the reports.

1. Serious events include any event or condition that is life threatening or results in a hospitalization or a physical or cardiac event serious enough to require medical attention. These events may be:

- a. Fatal
- b. Life threatening

- c. Permanently disabling
- d. Required or prolonged hospitalization (admission, not ER visit)
- e. Overdose
- f. Significant hazard to the patient

2. Non-serious events include all other events.

D. This is a single site study.

E. Ongoing assessments that may impact the safety or ethics of the study.

The research team is active in clinical pain research and will continue to monitor the literature, attend national and international conferences, and consult with colleagues to assure that we are aware of any emerging data that may impact the safety or the ethics of the study.

F. Advanced plans for interim/futility analysis

One focus of the investigator meetings will be to continuously monitor and develop strategies to prevent adverse reactions, monitor the research staff, and protect data integrity. Accrual data will be reviewed by the team and the UTHealth IRB. The study team will make amendments to the protocol should accrual fall below 15% of the target or should drop-outs exceed projections by 15%.

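### Do the differing rules on relatedness, seriousness and safety-committee review make the trial's safety results depend on which section is followed?

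*Combined protocol and SAP*

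**What the plan says.** Three topics are each described in more than one place in the combined protocol and SAP.

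- **Relatedness.** Under Study Procedures, the side-effects text following Acceptability says that for any reported side effect "the degree of relatedness to the intervention will be assessed on a 5-point scale", and refers to the monitoring plan, in a Human Subjects section, for details. Section C (Adverse Events and Unanticipated Problems) has the investigative team and the SMC classify events by seriousness, "as well as 'non-attributable,' 'possibly attributable,' or 'attributable' to the intervention".
- **Seriousness.** The lead sentence of the definition in section C includes "a physical or cardiac event serious enough to require medical attention". Item d of the list beneath it reads "Required or prolonged hospitalization (admission, not ER visit", closing the bracket there. Whatever is not serious is non-serious.
- **SMC review.** Section A (Monitoring Entity) says "should any adverse event occur, the SMC will be informed immediately, and a special session will be scheduled". Section B1 says "All adverse events will be reviewed monthly by the research team and annually by the SMC".

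**The concern.** Read quickly, each pair seems to treat the same event in two ways. A tingling complaint could carry one of five relatedness grades or one of three. A cardiac event treated in an emergency room without admission could be serious by the lead sentence and not serious by item d. A mild event could call an SMC session at once or wait for the yearly review.

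This would matter because the side-effects questionnaire is a named secondary outcome and the plan describes the study as minimal risk. If counts of related or serious events moved with the section a rater had open, the safety summary would not be reproducible. And if every sensation elicited after stimulation called for a special session, the committee could be overloaded and miss events that deserve attention.

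**Working it through.** No formula tests this point. It turns on reading the sections together, with one piece of arithmetic on committee load.

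**1. Relatedness.** The two scales belong to different instruments.

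- The 5-point rating attaches to side effects reported at the end of each stimulation session, where presence and severity are scored 0-10.
- The three categories attach to events recorded in the adverse events and unanticipated problems log, and are assigned by the team and the SMC together.

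A finer rating on a form and a coarser adjudication on a log are compatible. The plan does not say how one maps to the other. The Human Subjects section that the side-effects text points to is not part of the available text, so a mapping there can be neither confirmed nor ruled out.

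**2. Seriousness.** Take a cardiac event treated in an emergency room without admission.

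- Does it count as hospitalization? No, by the bracket in item d.
- Does it meet the limb of the lead sentence on physical or cardiac events that need medical attention? Yes.
- Does item d remove it from that limb? No. The bracket qualifies the word hospitalization and nothing else. The list is introduced permissively, and item f (significant hazard to the patient) is a further route.
- Does it fall into the residual non-serious class? That class holds only events that are not serious, so an event meeting the lead sentence is not in it.

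The text therefore does not classify this event both ways. The drafting is loose because no list item mirrors the medical-attention limb.

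**3. SMC review.** Section A first says the committee meets before enrollment, then yearly, and also when needed to adjudicate adverse events. It later introduces the special session as an addition to the yearly meetings. Section B1 and the reviewing paragraph of section C describe the periodic review, and neither says it is the only one. Annual and event-driven meetings are both planned. What differs is the breadth of the trigger: any adverse event in one sentence, as needed in another.

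**4. Committee load.** Inputs: 120 participants (Study Population), and 10 sessions (Study Design, two weeks of weekdays) or 15 (Study Procedures, three weeks). Those two durations contradict each other and must be reconciled, but that is a separate matter.

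- Questionnaires: 120 × 10 = 1,200, or 120 × 15 = 1,800.
- At an assumed 10% reporting rate on the lower count: 0.10 × 1,200 = 120.
- At an assumed 30% on the higher count: 0.30 × 1,800 = 540.

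To turn 120-540 reports into 120-540 special sessions takes three conditions: the 10-30% rate, every questionnaire sensation counting as an adverse event, and a separate session for each event. The plan gives no rate. It collects sensations such as tingling and itching as side effects on the questionnaire, while section B1 separately has participants asked about adverse events at each stimulation. Nothing stops one session from covering several events.

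**5. Does any result move?** The side-effects outcome uses presence and 0-10 severity; the section C labels do not enter it. The Statistics section names no analysis of serious or attributable events. Section F ties protocol amendments to accrual and drop-out, and early termination for unexpected adverse events is left to SMC recommendation with no numerical boundary. No stated figure depends on which wording is used.

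**The case for a change.** The best case for acting is that the plan does carry two relatedness scales with no link between them, and does not say when a questionnaire side effect becomes a logged event. In a population aged 50-85, emergency-room visits without admission are foreseeable, and a rater working from the list alone could code one differently from a rater working from the lead sentence. Taken literally, the trigger in section A is broad enough that staff will apply some unwritten threshold. Reporting times to the IRB also differ: immediate for procedure-related reactions under Role of the IRB, within one week under section C. Aligning the wording would cost almost nothing.

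Much of this stands as a description of the drafting. The missing mapping is real, and so is the uneven wording of the SMC trigger. What does not stand is the step from there to altered safety results. Seriousness and attribution are assigned through one process, with the team and the SMC acting together, so there are not two competing sets of classifiers. Meeting dates and reporting times affect oversight and cannot change how an event is counted. Narrowing immediate SMC notice to serious or unexpected related events would go beyond reconciliation: it would substitute a different reporting rule for the plan's own, and Data and Safety Monitoring ties the committee's operations to NIH and NINR policy that is not reproduced in the document.

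**Conclusion.** The concern does not call for a change to the plan. Of the three apparent conflicts, one is a genuine mismatch of scales that can coexist, one comes from reading a qualifier on hospitalization as an exclusion from seriousness, and one treats two complementary meeting schedules as alternatives. The effect on the efficacy analysis, the stated power and the side-effects outcome is nil. The 120-540 figure is a product of assumptions and does not measure a burden the plan creates.

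This rests on two readings: that the 5-point rating belongs to the session form and the three categories to the event log, and that the serious-event list illustrates its lead sentence. Both are the natural readings, though neither is spelled out. The plan provides for a manual of procedures on data collection and quality assurance, to be written at start-up. That is the ordinary place to record how form ratings carry over to the log, and the shared classification step gives the team and the SMC the occasion to apply one convention to every participant. Were safety tables by relatedness planned as a formal comparison, or a stopping rule set on counts of serious events, the missing mapping would carry more weight; neither is in the plan.

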### **Data and Safety Monitoring**

- The DSM plan is in accordance with the Policy of the National Institute of Nursing Research (NINR) for Data and Safety Monitoring of Extramural Clinical Trials set forth in 2014. As part of the DSM plan, we have convened a Safety Monitoring Committee (SMC) of which the organization, responsibilities, and operations are mandated by NIH and NINR policy.
- Level of risk of the intervention. We will investigate the effects of self-administered transcranial direct current stimulation (tDCS) on clinical pain in older adults with knee osteoarthritis pain in this study. The FDA determined that the tDCS device as used in those studies is Non-Significant Risk (NSR), and the UTHealth IRB also determined that the tDCS as used in this study is Non-Significant Risk (NSR). To add additional safety measures for this study, we will convene a SMC. This study constitutes minimal risks because: (1) the discomfort is transient in nature and generally subsides immediately after the procedure; (2) participants are instructed that they may stop any procedure at any time with no adverse consequences; and (3) the level of discomfort experienced by participants is below their tolerance level. Also, risks will be minimized by adhering to our exclusion criteria, and the study physician will have full discretion to exclude participants who may be at excessive risk.

#### **A. Monitoring Entity**

Role of the PI and investigative team. [name], the PI, will have primary responsibility for monitoring study research staff, who will receive training on the study design, recruitment, and protocol prior to study initiation. Research staff will receive formal training on the study protocol by Drs. [name], [name], and [name], which will entail one day of intensive training followed by additional training sessions as needed. The research staff will attend weekly meetings with the PI and monthly team meetings during data collection with the PI and co-investigators to discuss any study issues regarding recruitment and follow-up data collection. These meetings will be used to discuss experiences with the intervention participants, provide consultation, ascertain whether the research staff are following study protocols,

evaluate and reinforce cultural competence, and identify any potential adverse events. [name], the study statistician, will coordinate data management and analysis.

**Role of the SMC.** The SMC will be responsible for oversight of the activities related to implementing the clinical trial to ensure patient safety, conformance to the clinical protocol, overall performance of the trial components, and integrity of the data being collected. The SMC will meet prior to the start of enrollment, and then annually to review study progress (e.g., recruitment, retention, and safety procedures) and participant safety concerns and also as needed to adjudicate any adverse events. All meeting materials will be considered privileged by SMC members. This confidentiality will be maintained at all times to the extent permitted by law.

The SMC will comprise 3 members with expertise in neuromodulation, statistics, and geriatric clinical research: [name], professor of psychiatry and behavioral sciences at Baylor College of Medicine; [name], PhD, associate professor and biostatistician at The University of Texas Health Science Center at Houston Cizik School of Nursing; and [name], Roy M. and Phyllis Gough Huffington Chair in Gerontology and the Nancy P. and Vincent F. Guinee Distinguished Chair in Gerontology at The University of Texas Health Science Center at Houston. The SMC members are independent of the project. These members are appropriately qualified to review the scientific design and conduct of the study, to evaluate safety and risks to participants, to interpret data statistically, and to make recommendations concerning continuation, modification, suspension, or termination of the study.

Annual SMC meetings will begin after the first week of data collection. In addition, should any adverse event occur, the SMC will be informed immediately, and a special session will be scheduled to discuss strategies to deal with the event. The annual meeting will include a synopsis of the protocol and design, discussion of the status of interventions and data collection procedures, a summary of subject contacts, discussion of any adverse events or potential adverse events, status of data entry and verification, and a summary of any descriptive and inferential statistics to date. Details about data quality and completeness and data collection timeliness will be provided to the SMC, including enrollment rates, exclusion rates and reasons, completion of scheduled data collection, reasons for study withdrawal, adequacy of enrollment composition, demographic similarities/differences between the intervention and control groups, protocol deviations and adherence, and compromises in confidentiality. The SMC meetings will be closed sessions without the investigators, during which the SMC will discuss the need for additional procedures to prevent adverse events or ensure data integrity. In the unlikely case that the study needs to be terminated early owing to unexpected adverse events or inadequate conduct of the study, the SMC will make recommendations to the investigators.

Recommendations from the SMC meetings will be shared with the UTHealth IRB and the NIH during annual reports and immediately if the SMC identifies adverse events not previously reported or recommends early termination of the study.

**Role of the IRB.** This study will be approved by the UTHealth IRB. The UTHealth IRB will have the primary oversight of the study, and the PI ([name]) will be responsible for reporting the status of the study to the IRB. Annual progress reports and renewals will be completed for the IRBs and will include a summary of the recommendations of the SMC. If adverse reactions related to study procedures are noted, they will be immediately reported to the UTHealth IRB by [name] so that the IRB is aware of any risks involved with the study. The IRB will be responsible for ensuring the adequate and appropriate composition of the SMC as specified by NINR policy.

**Reporting to NINR.** [name], the PI, will be responsible for submitting necessary reports to the NINR. Summaries of the protocol and design, the status of the intervention group, data collection procedures, a summary of subject contacts, discussion of any adverse reactions or any potential adverse reactions, the status of data entry and verification, a summary of any descriptive statistics to date, and the recommendations of the SMC will be included in each annual report to the NINR. The NINR will be

notified within 7 days if the human subjects research or the DSM plan is changed prior to or during implementation of the clinical trial for approval. In addition, should any adverse reaction occur or should the SMC recommend terminating the study early, the information will be immediately reported to the NINR program officer. All personal identifiers will be removed from any documentation sent to the NINR. Timely reports to the NINR will be generated for:

- Unanticipated problems or unexpected serious adverse events that may be related to the study protocol
- IRB-approved revisions to the study protocol that indicate a change in risk for participants
- A summary of recommendations made by the SMC or other monitoring entity as appropriate and (if applicable) the action plan for response
- Notice of any actions taken by the IRB or regulatory bodies regarding the research and any responses to those actions

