Data quality control. All staff involved in data collection will be trained and certified to ensure their competence and re-certified periodically throughout the study, as we have done in similar trials. Data will be collected and numerically coded using pre-tested electronic entry forms. Every effort will be made to ensure that missing data are kept to a minimum. Data entry programs with range checking and response validation will be used for all data entered. The research assistant will be trained to avoid omissions in data entry, and computer entry protocols will be programmed to avoid accidental skipping of question items. As we have done in prior studies, we will develop a manual of procedures during the initial study start-up period that explicitly describes the specific procedures related to intervention delivery, data collection, and quality assurance.

Measurement and reporting of participant accrual and adherence to eligibility criteria. The rate of participant accrual as well as adherence to inclusion/exclusion criteria will be reviewed weekly during the recruitment phase and then every month to assure that participants meet the eligibility criteria and ethnic diversity goals outlined in the grant proposal.

Final storage of paper data. All paper data (e.g., consent forms) will be housed at a facility that specializes in the storage of medical/research information. The destruction date of these files will be at least 7 years from the termination of the study and will be authorized by the PI.

Access to cleaned computer data. Once the study is complete and all data have been collected, entered, and passed the audit process, the data will be available to the PI and his designates for analysis. Only the PI can give permission for the release of aggregated study data. No confidential information may be released without the express written consent of the study participants. Only copies of the finalized data will be released. The original data file will remain in its pristine state.

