### **Statistics**

- In this study, we will randomly assign 120 individuals to two groups, i.e., 60 participants to each group. With this sample size, we will be able to detect the expected effect size of 0.89 with more than 99% power at a significance level of 0.05 after accounting for 10% attrition. The minimum effect size we can detect with this sample size is 0.54 with 80% power at a significance level of 0.05 after accounting for 10% attrition. Thus, our sample size will provide sufficient power to detect a clinically meaningful effect.
- All data will be analyzed using the intention-to-treat approach. All demographic and clinical variables will be summarized using descriptive statistics, such as mean  $\pm$  standard deviation (SD) or median (interquartile range, IQR) as appropriate for continuous variables and frequency and percentage for categorical variables. The distribution of all variables will be examined to check the validity of distribution assumptions before any analysis, using measures of central tendency and a visual inspection of histograms and quantile-quantile plots. If the normality assumption is not met, equivalent non-parametric approaches will be employed. SAS 9.4 (SAS Institute, Cary, NC) will be used to perform the proposed statistical analyses.

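### Does putting inferential statistics on the safety committee's annual agenda leave the final 0.05 test unprotected?

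*Combined protocol and SAP*

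**What the plan says.** Under Data and Safety Monitoring, A. Monitoring Entity, the annual SMC meeting covers protocol status, data collection, adverse events, data entry and "a summary of any descriptive and inferential statistics to date". The same section fixes the calendar ("The SMC will meet prior to the start of enrollment, and then annually to review study progress") and places the first annual meeting after one week of data collection. The committee oversees the trial "to ensure patient safety, conformance to the clinical protocol, overall performance of the trial components, and integrity of the data being collected". Its members are described as qualified "to make recommendations concerning continuation, modification, suspension, or termination of the study". The one sentence on stopping concerns a study "terminated early owing to unexpected adverse events or inadequate conduct of the study".

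Section F of the monitoring plan has interim and futility analysis in its title. It deals with adverse reactions, staff monitoring, data integrity, accrual and drop-out. Its only numerical triggers are for accrual and drop-out: "The study team will make amendments to the protocol should accrual fall below 15% of the target", or if drop-outs pass projections by 15%. It contains no test, timing or boundary.

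The Statistics section uses one significance level throughout, for example a minimum detectable effect of 0.54 "with 80% power at a significance level of 0.05" after 10% attrition.

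**The concern.** Inferential statistics, as an agenda item with no outcome named, could include between-arm tests of the pain NRS or the fNIRS response. The committee can recommend modification or termination. The section where a reader would look for an interim plan neither gives one nor says that none is intended. The parallel list for the annual NINR report mentions descriptive statistics only, so the SMC wording goes further than its sister passage.

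Repeated tests at 0.05 that can each end the trial raise the false-positive rate above 5%, and the sample-size calculation reserves nothing for them. In a double-blind trial with a self-reported primary outcome, a reader would want to be sure that the final test was the only efficacy test.

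**Working it through.** **1. The plan's own figures.** Inputs from the Statistics section: 60 per arm, 10% attrition, level 0.05. Evaluable per arm: 60 × 0.9 = 54. Two-sided testing is assumed, since sidedness is not stated.

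- Minimum detectable effect = (1.960 + 0.842) × √(2/54) = 0.539, against the stated 0.54.
- Power at 0.89 = Φ(0.89 × √27 − 1.960) = Φ(4.625 − 1.960) = 99.6%, against the stated figure of more than 99%.

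Both reproduce (a t-test gives 0.544 and 99.6%). The design is a fixed-sample, two-sided 5% test with nothing set aside for interim looks.

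**2. What acted-on looks would cost.** This is hypothetical, because the plan gives neither the number nor the timing of informative looks. Over three years with annual meetings, the first of them carrying almost no data, one or two is a reasonable guess. Under the null the look statistics are jointly normal with correlation √(t₁/t₂) for information fractions t₁ < t₂. Type I error is 1 − P(|Z| ≤ 1.960 at every look), found by recursive numerical integration.

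| Looks before the final test | Information fractions | Type I error |
|---|---|---|
| None, or none acted on | – | 5.0% |
| One | 0.5 | 8.3% |
| One | 0.2 / 0.8 | 9.2% / 7.1% |
| Two | 1/3, 2/3 | 10.7% |
| Two | 0.2, 0.6 / 0.33, 0.9 | 11.5% / 10.0% |

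**3. Which row the plan is in.** To leave the first row, three things must all happen: a between-arm efficacy test is run, it is judged at p<0.05, and its result changes the course of the trial.

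- *Test run.* No passage schedules one. The item covers whatever statistics exist. It also has other uses: the same paragraph asks for demographic similarities and differences between the groups, and section B1 wants minority status and gender in the adverse-event reports so that differential effects can be detected.
- *Judged at 0.05.* No interim criterion of any kind is given.
- *Acted on.* The remit and the termination sentence cover safety and conduct. The closed session is for discussing further procedures to prevent adverse events or ensure data integrity. Section F lists no efficacy or futility trigger.

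Followed as written, the plan stays in the first row. A recommendation to stop for harm or poor conduct is not a claim of efficacy and uses no alpha.

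**4. Whether tighter wording would gain anything.** Striking the inferential item would also take safety and baseline comparisons away from a committee chosen partly for statistical expertise, and would still leave descriptive efficacy results by arm unrestricted. An interim limit of p<0.001 with 0.05 kept at the end gives 5.02% for one look at half information, 5.05% for two at thirds and 5.14% for two at 10% and 20%. That is slightly worse than the 5.0% the plan has now, and it guards a look nobody has planned.

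**The case for a change.** The strongest reply is that a conditional item without limits is still a permission. The stopping sentence names safety and conduct but does not say that these are the only grounds, and the committee may also recommend modification. Closed sessions and privileged materials control who sees results, not what is tested. The plan does not say who prepares the summaries or whether they are split by arm. On this view a short statement would cost nothing and would settle the matter.

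The factual part stands: no sentence excludes interim efficacy testing, and section F does not deliver what its title suggests. What does not follow is that the error rate is at risk under the plan. Silence about a look, in a document whose remit and stopping grounds are all safety and conduct, is most naturally read as no look.

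It can also be argued that annual inferential summaries clash with section B2, under which, once "all data have been collected, entered, and passed the audit process, the data will be available to the PI and his designates for analysis". This is not a contradiction. That sentence governs release of cleaned data to the investigators, while the SMC meets without them and its materials are privileged.

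**Conclusion.** No change is needed. The agenda phrase is loose and the title of section F promises more than the section holds, but these are gaps in wording that an SMC and a trial statistician working to the stated remit would fill in the ordinary way: no efficacy stopping, and one efficacy test at the end. The size of the problem under the plan as written is zero, with type I error at 5%. The 7% to 12% range belongs to a scenario the document does not describe, in which one or two unadjusted between-arm efficacy looks are acted on at p<0.05. The conclusion rests on two assumptions: that the SMC keeps to the remit and termination grounds given in section A, and that the final analysis is the two-sided 0.05 test that reproduces the stated power.
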